Long term (several weeks to several months) studies are required to investigate and to compare the incorporation of n-3 fatty acids into transport pools (blood lipids) and functional pools (e.g. cells) which is a true measure of n-3 status. When included in the human diet EPA and DHA are incorporated into plasma lipid fractions, platelets, white cells, red cells and many other cell and tissue types. We have studied the detail of such fatty acid incorporation, particularly for plasma phospholipids and for white blood cells in at least eight studies in human volunteers and also in patients with advanced atherosclerosis and with Crohn's Disease. In these studies fish oil supplements of various types (but almost exclusively in the TAG form) have been used with blood being sampled at various time intervals over the course of several months. We have reported both the time- and dose-dependent nature of the incorporation into plasma phospholipids and white blood cells (e.g. see [21]). Incorporation of EPA and DHA is typically detectable within weeks. However the rate of incorporation and the time to reach a maximum varies according to turnover of the pool investigated. Thus incorporation into white cells is faster than into red cells. We will use the general approach used in our previous studies with human volunteers to investigate the appearance in plasma lipids (phospholipids, TAGs, cholesteryl esters, NEFAs, EEs), in white cells (mononuclear cells) and in red cells of EPA and DHA when supplemented in the TAG or EE or FFA form.

Subjects and supplements

Healthy males and females aged 18 to 45 years with a body mass index between 20 and 32 kg/m^2 (n = 100) will be recruited. Subjects will recruited via posters; email shots in the University of Southampton, Southampton General Hospital, and other organisations with which the researchers have contact; advertisements in local newspapers. Subjects who express an interest will be screened by telephone interview. If they fit the inclusion and exclusion criteria (see below) they will be sent the information sheet. They will be contacted about 7 days later to confirm their interest or not, and if they remain interested an appointment will be made for them to visit the Wellcome Trust Clinical Research Facility, Southampton General Hospital.

Recruited subjects will be randomised to one of five groups (n = 20 per group):

- Placebo
- Omega-3 ethyl esters
- Omega-3 free fatty acids

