- Omega-3 triglycerides (standard formulation)
- Omega-3 triglycerides (interesterified formulation).

The n-3 fatty acid preparations to be used are all commercially available as supplements and will be provided in capsules. Approximately 1.5 g EPA plus DHA (approx. 1.1 g EPA and 0.4 g DHA) will be given per day. Subjects, researchers and clinical staff will be blinded to group allocation.

Inclusion criteria

- 1. Aged 18 to 45 years
- 2. Body mass index 20 to 32 kg/m^2
- 3. Not consuming fish oil or other oil supplements
- 4. Not eating more than one oily fish meal per week
- 5. Willing to adhere to the study protocol
- 6. Being able to provide written informed consent

Exclusion criteria

- 1. Aged < 18 or > 45 years
- 2. Body mass index $< 20 \text{ or} > 32 \text{ kg/m}^2$
- 3. Being diabetic (type 1 or type 2)
- 4. Use of prescribed medicine to control inflammation
- 5. Chronic gastrointestinal problems (e.g. IBD, IBS, celiac disease, cancer)
- 6. Allergic to fish
- 7. Participation in another clinical trial
- 8. Use of fish oil or other oil supplements

Subject participation schedule

Subjects who express an interest will be screened by telephone interview. If they fit the inclusion and exclusion criteria they will be sent the information sheet. They will be contacted about 7 days later to confirm their interest or not and if they remain interested an appointment will be made for them to visit the Wellcome Trust Clinical Research Facility, Southampton General Hospital. At the first (and all subsequent) visit, subjects will attend in the fasted state (no food or drink except water after 9 pm the previous evening).

Subjects will visit the Wellcome Trust Clinical Research Facility, Southampton General Hospital on six occasions each between 8 and 10 am. On each occasion they will be in the fasted state. Visits will be at study entry and after approx. one, two, four, eight and twelve weeks of supplementation. On each occasion blood (20 ml) will be taken into heparin; at the visit made at study entry height and weight will be measured. At the end of each visit subjects will be offered toast and a hot drink. Subjects will receive a supply of supplements along with instructions on how to take them at the first study visit.

Sample analysis

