Blood will be used to prepare plasma, mononuclear cells and red cells. Plasma will be aliquoted and frozen at minus 80°C. Mononuclear cells will be frozen at minus 80°C. Red cell membranes will be prepared using standard techniques currently in use in the PI's lab and then frozen at minus 80°C. Lipid will be extracted from plasma, mononuclear cells and red cells using chloroform/methanol. Plasma TAGs, PLs, NEFAs and EEs will be isolated by solid phase extraction [21]. The fatty acid composition of plasma TAGs, PLs, NEFAs and EEs and of mononuclear cells and red blood cells

will be determined by gas chromatography. Inflammatory marker concentrations in blood will be measured by flow cytometry.

10. Data handling and record keeping

- All data will be entered onto a spreadsheet (Microsoft Excel) by the researchers involved.
- All data will be entered on a password-protected computer. This data will be accessed only by the PI and the researchers involved.
- All data will only be linked to study codes and thus not identifiable with the source volunteer. However, the caveat to this will be a data set recording the volunteer name and study code without any other volunteer details.
- All data recorded on paper will be kept in a locked filing cabinet in the researchers' office and/or in a dedicated, restricted access, clinical data storage area on Level D of the IDS Building, University of Southampton.
- Data of an identifiable nature (i.e. volunteer names, contact details, addresses) will be destroyed 12 months after the end of the study. All other data will be kept securely for 15 years and then destroyed.
- Data will be obtained, handled and stored in adherence to the principle set out in the Data Protection Act 1998.
- The investigators and the Institute of Human Nutrition will permit monitoring, audits, REC and MHRA review (as applicable) and provide direct access to source data and documents.

11. Statistical Analysis

The statistical analysis will involve:

- comparison of the change in EPA content of plasma phospholipids from study entry to week 12 between the different treatment groups (the primary outcome). This will be performed by one factor ANOVA.
- comparison of the change in EPA content of each of the other plasma lipid pools and of mononuclear cells and red blood cells from study entry to week 12 between the different treatment groups (the primary outcome). This will be performed by one factor ANOVA.

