- comparison of the change in DHA content of each of the plasma lipid pools and of mononuclear cells and red blood cells from study entry to week 12 between the different treatment groups (the primary outcome). This will be performed by one factor ANOVA.
- comparison of the change of the EPA and DHA contents of each plasma lipid pool and of mononuclear cells and red blood cells over time following consumption of n-3 fatty acids in each chemical form. This analysis will be performed using two-factor repeated measures ANOVA, the two factors being time and group (i.e. "treatment").
- comparison of the change over time in blood concentrations of inflammatory markers according to treatment group. This analysis will be performed using two-factor repeated measures ANOVA, the two factors being time and group (i.e. "treatment").

All statistical comparisons will be performed at the end of the study using SPSS.

12. Sample size calculation

The study is powered according to the anticipated change in EPA content of plasma phospholipids (this is similar to the anticipated change in EPA in mononuclear cells and in red cells). Based upon previous studies of this sort, a supplement providing 1.1 g EPA/day is expected to increase the EPA content of plasma phospholipids by 100% from approximately 1 to approximately 2% of total fatty acids. It is considered that a 25% lower incremental increase in EPA content is meaningful. Typical standard deviations for the incremental increase in EPA content of plasma phospholipids from our previous studies are approximately 0.25%. Thus, sample size was calculated using mean values of 1 and 0.75 for the two groups, respectively, and standard deviations of 0.25 for each group. A sample size calculator revealed that a sample size of 17 per treatment group will give 90% power of

detecting this effect (i.e. a 25% increase) as statistically significant, by a pairwise comparison and setting P < 0.05, as is usual. In order to allow for a drop-out rate of 20% 20 subjects per group will be recruited (100 subjects in total).

13. Safety assessments

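### The primary ANOVA of change has no baseline covariate; adding study-entry EPA should maintain or improve precision, by an amount the protocol's figures do not determine

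*Protocol*

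**What the plan says.** Protocol section 11 (Statistical Analysis) defines the primary analysis as a "comparison of the change in EPA content of plasma phospholipids from study entry to week 12 between the different treatment groups (the primary outcome"), and adds: "This will be performed by one factor ANOVA". The single factor is treatment group, and no covariate is named. The same model is set for EPA in the other plasma lipid pools, mononuclear cells and red cells, and for DHA in all of these, with the change in each case compared "from study entry to week 12 between the different treatment groups (the primary outcome). This will be performed by one factor ANOVA".

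The baseline value is available. Section 9 (Subject participation schedule) states: "Visits will be at study entry and after approx. one, two, four, eight and twelve weeks of supplementation". It also states: "On each occasion blood (20 ml) will be taken into heparin". The week-12 and entry samples go through the same gas chromatography (section 9, Sample analysis).

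On design: "Recruited subjects will be randomised to one of five groups (n = 20 per group"). Section 12 bases the sample size on the change itself: "sample size was calculated using mean values of 1 and 0.75 for the two groups", with an SD of 0.25 for the incremental increase, 17 per group for 90% power, and 20 recruited per group to allow for 20% drop-out.

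**The concern.** Analysing change by one-factor ANOVA is the same as regressing week-12 EPA on group and entry EPA with the entry slope held at 1. If the true slope is not 1, change remains correlated with baseline, and two things follow.

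- The residual variance is larger than it need be.
- In the trial as realised, a chance difference in mean entry EPA between two groups shifts their contrast by (slope − 1) × the difference.

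Entry EPA can be expected to vary between subjects, since the inclusion criteria allow up to one oily fish meal a week. With about 16 to 20 per group, chance imbalance is not negligible. At stake is the precision of the comparison between formulations, in a trial with little to spare.

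**Working it through.** **Inputs from the protocol (section 12).** Difference 1 − 0.75 = 0.25; SD of change 0.25; P < 0.05 pairwise, taken as two-sided because no side is stated; 17 per group; 20 recruited with 20% drop-out.

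**Inputs that must be assumed.** r, the correlation of entry and week-12 EPA; and k = SD(week 12)/SD(entry). The protocol gives neither, and gives no SD at either visit.

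**Step 1: the plan's own figure.** Standardised difference d = 0.25/0.25 = 1. Two-sample t-test power uses df = 2n − 2 and non-centrality d × √(n/2).

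- n = 17: power 80.7%, not the stated 90%. A t-test needs 23 per group for 90%.
- n = 16 (20 × 0.8 = 16): power 78.1%.

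This calculation already uses the SD of change, so it describes the change-score analysis as planned.

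**Step 2: effect of estimating the slope.** With s the entry SD:

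- Var(change) = s²(1 + k² − 2rk)
- Residual variance under ANCOVA = s²k²(1 − r²)
- Ratio V = k²(1 − r²)/(1 + k² − 2rk), which becomes (1 + r)/2 when k = 1
- Slope of week 12 on entry = rk; V = 1 exactly when rk = 1

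Holding the SD of change at 0.25, the ANCOVA residual SD is 0.25√V. One degree of freedom is removed for the covariate. For example, at k = 1 and r = 0.5, V = 0.75 and the residual SD is 0.25 × √0.75 = 0.2165.

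**Step 3: power at 16 per group** (change-score analysis: 78.1%).

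| k | r = 0.3 | r = 0.5 | r = 0.7 | r = 0.9 |
|---|---|---|---|---|
| 1 | 92.4% | 88.4% | 84.3% | 80.1% |
| 1.5 | 83.4% | 79.5% | 78.1% | 87.3% |
| 2 | 79.8% | 78.0% | 81.0% | 96.0% |

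The gain vanishes where rk is near 1: k = 1.5 with r = 0.7 (slope 1.05), or k = 2 with r = 0.5 (slope 1.00). In the second case the lost degree of freedom costs about 0.1 point.

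**Step 4: shift from chance imbalance.** Take k = 1, 16 per group, and an imbalance of one standard error, s√(2/16). With the SD of change at 0.25, s = 0.25/√(2(1 − r)).

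- r = 0.5: s = 0.25; imbalance 0.25 × 0.354 = 0.088; shift 0.5 × 0.088 = 0.044 in absolute size.
- r = 0.7: s = 0.323; imbalance 0.323 × 0.354 = 0.114; shift 0.3 × 0.114 = 0.034.

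These are about 18% and 14% of the 0.25 difference that section 12 calls meaningful. Where the slope is near 1 the shift is near zero.

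**The case against.** The strongest reply is that nothing here is an error. Under randomisation, the ANOVA of change is valid and unbiased over repeated trials, and it matches the scale on which section 12 sizes the trial. That stands, and the point is one of efficiency.

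Three stronger readings are tempting, and the protocol does not support them.

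- **That the plan ignores baseline.** It does not, since a change score subtracts it. What is missing is an estimated slope.
- **That the change-score analysis is why the trial falls short of 90% power.** It is not. The calculation already uses the SD of change, so nothing is lost against the plan's own basis. The shortfall comes from the sample-size arithmetic (17 per group gives about 81%) and from the drop-out allowance (20 less 20% leaves 16, not 17). ANCOVA may offset the shortfall but does not correct it.
- **That a large gain is assured.** Equal SDs are an assumption. Section 12 expects mean EPA to double from about 1% to about 2%, so a larger SD at week 12 is quite possible. The strength, and even the sign, of the correlation between baseline and change cannot be read from the document.

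It may also be said that a statistical analysis plan, not shown, could add the covariate. But section 11 does not leave the primary model open; it names one without a covariate, so such a plan would have to depart from the protocol. Finally, ANCOVA assumes a common slope, which may differ between placebo and active arms. That is a fair caution, but no reason to fix the slope at 1 in every arm.

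**Conclusion.** The point holds as a recommended improvement to a valid analysis. In large samples, ANCOVA on study-entry EPA has residual variance no greater than that of the change-score analysis in this randomised design. It also removes the linear effect of chance baseline imbalance, and the data are already collected. With equal SDs and 16 per group, the gain is about 2 points of power at r = 0.9, 6 at 0.7, 10 at 0.5 and 14 at 0.3; with unequal SDs it runs from nil upward. All these figures rest on assumed r and k, a two-sided 5% test, and the protocol's SD of 0.25 for change. The direction is well founded; the size cannot be determined from the protocol.

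**What to change.** In section 11, replace the one-factor ANOVA for the week-12 comparisons with wording such as: *week-12 EPA content of plasma phospholipids will be compared between treatment groups by ANCOVA, with group as factor and study-entry EPA content of plasma phospholipids as covariate*. Make the same change for EPA in the other pools and for DHA, each adjusted for its own study-entry value. Using change as the response with the same covariate gives identical group contrasts.

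State the common-slope assumption and prespecify a check of it between placebo and active arms. Settle the wording before any results are seen, because a covariate added afterwards is open to challenge. Adjusting for body weight, also recorded at entry ("at the visit made at study entry height and weight will be measured"), is a matter of preference and not part of this point.

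The cost is one degree of freedom per model and a change of text; no new samples are needed and SPSS will still serve. The sample-size statement in section 12 needs its own correction.

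### Section 11 gives three different sets of week-12 comparisons (12 to 14 tests) the single primary-outcome label, while section 12 sizes the trial on plasma phospholipid EPA alone

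*Protocol*

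**What the plan says.** Protocol section 11 (Statistical Analysis) lists three comparisons of change from study entry to week 12. Each uses one-factor ANOVA and each is labelled as the primary outcome.

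- First bullet: "comparison of the change in EPA content of plasma phospholipids from study entry to week 12 between the different treatment groups (the primary outcome".
- Second bullet: "the change in EPA content of each of the other plasma lipid pools and of mononuclear cells and red blood cells".
- Third bullet: "comparison of the change in DHA content of each of the plasma lipid pools and of mononuclear cells and red blood cells".

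The second and third bullets share the words "mononuclear cells and red blood cells from study entry to week 12 between the different treatment groups (the primary outcome", so the label is explicit in both.

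Section 12 (Sample size calculation) uses one outcome: "The study is powered according to the anticipated change in EPA content of plasma phospholipids". It adds in parentheses that "this is similar to the anticipated change in EPA in mononuclear cells and in red cells". It gives no standard deviation for either cell type and says nothing about DHA or the other plasma pools.

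Section 9 lists the pools in two ways. Under the general approach they are "plasma lipids (phospholipids, TAGs, cholesteryl esters, NEFAs, EEs), in white cells (mononuclear cells) and in red cells of EPA and DHA". Under sample analysis they are "The fatty acid composition of plasma TAGs, PLs, NEFAs and EEs and of mononuclear cells and red blood cells", without cholesteryl esters.

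**The concern.** A singular label cannot belong to three different sets of outcomes. A reader of section 11 cannot tell whether the trial has one primary outcome or a dozen. A reader of section 12 would conclude that it has one.

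What is at stake is the claim the trial may make. Under the wording of section 11, a difference in red cell DHA or plasma NEFA EPA has the same standing as one in plasma phospholipid EPA. The choice among them could be made after the results are known. DHA, given at about 0.4 g/day against about 1.1 g/day of EPA, would be primary with no stated effect size, standard deviation or power.

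**Working it through.** **1. Number of tests carrying the label.** One omnibus ANOVA is counted per fatty acid and pool.

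| Bullet | Pools in section 9, sample analysis | Pools in section 9, general approach (adds cholesteryl esters) |
|---|---|---|
| 1: EPA, plasma phospholipids | 1 | 1 |
| 2: EPA, other plasma pools + 2 cell types | 3 + 2 = 5 | 4 + 2 = 6 |
| 3: DHA, all plasma pools + 2 cell types | 4 + 2 = 6 | 5 + 2 = 7 |
| Total | 12 | 14 |

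**2. What section 12 covers.** The stated inputs are increments of 1 and 0.75, SD 0.25, P < 0.05, 90% power and 17 per group. The standardised difference is 0.25 / 0.25 = 1. The figure of 17 comes out approximately if the test is one-sided: 17.13 before rounding, and 89.8% power at 17 by the normal formula. A two-sided t test at 17 per group gives 80.7%. That is a separate matter; here 17 serves only as the group size. The calculation covers one of the 12 to 14 outcomes. The remark on mononuclear and red cells extends it informally to three, all of them EPA.

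**3. Chance of at least one false-positive primary result.** Assumptions: each test at 5%, and all compared groups truly equal on every outcome. For k independent tests the chance is 1 − 0.95^k.

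- k = 12: 1 − 0.540 = 0.460
- k = 14: 1 − 0.488 = 0.512

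The outcomes come from the same subjects and capsules, so independence is unlikely. The protocol gives no correlations. The values below assume one common correlation and come from simulated F tests with 17 per group (20,000 trials per cell).

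| Assumed correlation | 5 groups, k = 12 | 5 groups, k = 14 | 4 active groups, k = 12 | 4 active groups, k = 14 |
|---|---|---|---|---|
| 0.3 | 41% | 46% | 40% | 45% |
| 0.5 | 33% | 37% | 34% | 37% |
| 0.7 | 25% | 27% | 25% | 27% |
| 0.8 | 20% | 21% | 20% | 22% |

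**4. When those rates apply.** The planned ANOVA has five groups, one of them placebo. Take section 12's increment of 1 in all four active groups and assume no change on placebo. The means are then 0, 1, 1, 1, 1, with grand mean 0.8, and the squared deviations sum to 0.64 + 4 × 0.04 = 0.80. The noncentrality is 17 × 0.80 / 0.25² = 217.6, and power on 4 and 80 degrees of freedom is essentially 100%. So even if the four forms were identical, the five-group test on plasma phospholipid EPA would be expected to reject, correctly, because of placebo. The rates in step 3 therefore need either equality of all five groups or a comparison restricted to the active forms.

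**5. Could all the outcomes stay primary?** Under Bonferroni the level would be 0.05 / 12 = 0.0042 or 0.05 / 14 = 0.0036. Two-sided t power at 17 per group for the planned pairwise difference would be 44.6% or 42.5%, and 90% power would need 37 or 38 per group. The planned size does not support that reading.

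**The case against.** The strongest reply is that the intended primary outcome is plain. The first bullet sets plasma phospholipid EPA apart from the other pools, section 12 sizes the trial on it, and the repeated phrase looks like a copying slip. That is probably right, and it makes this mainly a labelling correction. It does not make the text correct, and naming the primary outcome is a choice this protocol has made, not one it left to a SAP.

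Three stronger readings are tempting, and the protocol does not support them.

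- A reader might infer that every test is run at 5% with no adjustment. Section 11 gives no significance level; P < 0.05 appears only in section 12, for one pairwise comparison. A SAP may exist and may set an adjustment, so uncontrolled error is not established.
- A reader might infer a 46% to 51% false-positive risk whenever the omega-3 forms do not differ. Placebo is in the planned ANOVA, so equality of the forms alone does not produce that risk, and independence of the tests is also needed.
- A reader might say that outcomes other than plasma phospholipid EPA have no power basis at all. For EPA in mononuclear and red cells the protocol asserts a similar change, though without a standard deviation. For DHA the statement stands.

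**Conclusion.** Wrong as written. Section 11 contradicts itself by giving one primary label to 12 or 14 tests, and it disagrees with section 12, which makes a calculation for one outcome. That conclusion rests on the text alone. It needs correcting because it leaves open which result the trial may claim as primary.

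The error rates only illustrate the consequence: 46% to 51% if independent, roughly 20% to 46% at assumed correlations of 0.8 to 0.3. They depend on a 5% level per test, no adjustment, and true equality of all the groups compared. Even the low end is about four times the nominal 5%, but none of these figures is a property of the plan as stated.

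**What to change.** In section 11, keep the primary-outcome label on the first bullet only, in agreement with section 12. In the second and third bullets replace it with a secondary-outcome label. Make the change before unblinding.

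Multiplicity control for the secondary outcomes (Holm or false discovery rate, say) is optional and can be left to the SAP; it is not needed to remove the contradiction.

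The cost is a few words in two bullets, with no extra subjects, samples or assays. The downside is that DHA, and EPA outside plasma phospholipids, lose primary status.

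### Repeated measures ANOVA for the secondary time courses and inflammatory markers uses complete profiles only, although 20% drop-out is planned; a mixed model would keep the partial data at little cost

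*Protocol*

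**What the plan says.** Protocol section 11 lists five analyses. The first three compare the change from entry to week 12 between groups by one-factor ANOVA. They begin with the primary one: "comparison of the change in EPA content of plasma phospholipids from study entry to week 12 between the different treatment groups (the primary outcome". The fourth is the "comparison of the change of the EPA and DHA contents of each plasma lipid pool and of mononuclear cells and red blood cells over time", and the fifth is the course of the inflammatory markers. For both of these the method is fixed in the same words: "This analysis will be performed using two-factor repeated measures ANOVA, the two factors being time and group". On software, the section says: "All statistical comparisons will be performed at the end of the study using SPSS". It names no SPSS procedure, no sphericity correction and no levels for the time factor.

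Section 9 (Subject participation schedule) gives six unequally spaced visits: "Visits will be at study entry and after approx. one, two, four, eight and twelve weeks of supplementation". On allocation, section 9 says: "Recruited subjects will be randomised to one of five groups (n = 20 per group". On losses, section 12 says: "In order to allow for a drop-out rate of 20% 20 subjects per group will be recruited (100 subjects in total".

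**The concern.** The protocol names a method that, as usually run, needs a full set of visits from each subject, and it expects one subject in five to leave. Someone who withdraws after week 8 would then contribute nothing to the time course, although five of the six samples have been drawn and assayed.

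The early visits carry the information on rate of appearance, which section 8 sets out as objective 1 and which a week-12 change cannot show. For objective 2 (inflammatory markers) the repeated measures ANOVA is the only planned analysis.

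Two assumptions come with the method:

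- Complete-profile analysis is unbiased in general only if data are missing completely at random. Section 13 accepts that adverse events may lead to withdrawal and that subjects will not be asked why. Withdrawal related to the formulation could therefore not be ruled out from the data.
- The uncorrected within-subject F-test assumes sphericity. That is doubtful for an uptake curve sampled at weeks 0, 1, 2, 4, 8 and 12, where neighbouring visits are likely to be more alike than distant ones.

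**Working it through.** **Inputs.** From the protocol: 20 per group, 5 groups, 100 subjects; drop-out 20%; visits at entry and weeks 1, 2, 4, 8 and 12. Assumed, because the protocol gives no figure: the timing of drop-out, the rate of other missing samples, and the within-subject correlation.

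**1. Drop-out alone.** Complete profiles per group are at most 20 × (1 − 0.20) = 16, or 80 of 100 overall. The week-12 change analysis has the same 16.

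**2. What is discarded before week 12.** Spread the 20 drop-outs evenly over the five post-entry intervals, 4 in each (0.8 per group).

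| | Wk 1 | Wk 2 | Wk 4 | Wk 8 | Wk 12 |
|---|---|---|---|---|---|
| Subjects with a sample, per group | 19.2 | 18.4 | 17.6 | 16.8 | 16.0 |
| Used by complete-profile ANOVA | 16 | 16 | 16 | 16 | 16 |
| Ratio | 1.20 | 1.15 | 1.10 | 1.05 | 1.00 |

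Post-entry samples discarded: 4 × (0 + 1 + 2 + 3 + 4) = 40. The table agrees: 5 × (3.2 + 2.4 + 1.6 + 0.8) = 40. The loss is greatest at week 1.

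**3. Other missing samples.** Let m be the chance that a completer lacks the sample at any one of weeks 1, 2, 4 and 8. Section 14 defines completion by the last blood sample, so a completer has week 12 and the exponent is 4. Complete profiles per group = 20 × 0.80 × (1 − m)^4.

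- m = 2%: 16 × 0.98^4 = 14.8 (26% of the 20 lost)
- m = 5%: 16 × 0.95^4 = 13.0 (35% lost)

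**4. Precision of the entry-to-week-12 change.** I compared the variance from complete profiles with that from a likelihood model using all available visits. Drop-out timing is as in step 2, and correlation is assumed to be compound-symmetric or first-order autoregressive, 0.5 to 0.8.

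| Missing at weeks 1-8 | Variance ratio, complete profiles to mixed model |
|---|---|
| none | 1.07 to 1.12 |
| 2% | 1.16 to 1.21 |
| 5% | 1.31 to 1.37 |

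The mixed model's effective size is about 17.1 to 17.9 per group. This calculation takes the covariance as known and entry as part of the response, so it approximates the model proposed under the fix and slightly favours it.

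**5. Sphericity.** I simulated the uncorrected time-by-group F-test with 5 groups of 16, 6 visits, no true group effect and a nominal 5% level. The rejection rate was about 7% with autoregressive correlation 0.5 and between 9% and 10% with 0.8. It was between 10% and 11% when the correlation decays by a factor of 0.9 per week over the actual visit times. These correlations are assumptions.

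**The case against.** The strongest reply is that nothing here is false or contradictory. Repeated measures ANOVA is an accepted method. Epsilon corrections and multivariate tests come with it, and the handling of incomplete profiles and the coding of time are often left to a statistical analysis plan, which is not shown. With drop-out alone, the penalty at week 12 is only 7-12% in variance. The larger losses need missing-sample rates that the protocol does not give. A mixed model also rests on an untestable assumption.

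Most of that stands and limits the size of the point. It does not remove it, because the protocol itself fixes the method instead of leaving it open, and a more suitable one is available in the same software.

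Four stronger readings are tempting, and the document does not support them:

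- A reader might infer that all of objective 1 rests on this analysis. It does not. Three of the five bullets address EPA and DHA by one-factor ANOVA of the week-12 change, including the primary outcome, and are untouched.
- A reader might infer that entry is treated as an outcome and dilutes the treatment effect. The levels of time are not defined, and the bullets speak of change over time. Even with entry as a level, the interaction is a valid test of whether change differs between groups. Only the group main effect would shrink, and the protocol does not single that out as the test of interest.
- A reader might apply missing rates of 2-5% to all five post-entry visits on top of drop-out and report 28-38% lost. That counts week 12 twice; the figures are 26-35%, and they still depend on assumed rates.
- A reader might infer that the results will be biased. The protocol gives no evidence that tolerability differs between the forms. Bias is possible, not shown.

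**Conclusion.** The point holds as a worthwhile improvement to the two secondary repeated measures bullets. What follows from the protocol's own figures is that a complete-profile analysis uses at most 16 of 20 per group at every visit and sets aside samples already collected from those who leave. The figure of about 40 post-entry samples depends on even drop-out, and the range of 14.8 to 13.0 per group depends on the assumed 2-5% missing. The loss falls mainly on the early visits; at week 12 it is modest unless interim samples are also missing. The sphericity concern depends on the true correlation and would be met in part by a corrected test, to which the protocol does not commit. All of this supposes the usual complete-profile form of the method, since no SPSS procedure is named.

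**What to change.** In the fourth and fifth bullets of section 11 only, replace the two-factor repeated measures ANOVA with a linear mixed model for repeated measures, specified as follows:

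- **Outcome:** the values at weeks 1, 2, 4, 8 and 12.
- **Fixed effects:** group, visit as a category, group-by-visit, and the entry value of the same variable.
- **Within-subject covariance:** unstructured (5 × 6 / 2 = 15 parameters).
- **Subjects:** all randomised subjects with at least one post-entry sample.

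Under the even drop-out of step 2, four subjects leave before week 1, so this analyses 96 subjects and 96 + 92 + 88 + 84 + 80 = 440 post-entry samples. Complete profiles would give 80 subjects and 80 × 5 = 400 samples. The model also settles how the entry value is used and removes the sphericity assumption.

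Leave the primary analysis and the other week-12 one-factor ANOVAs as they are.

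The cost is a change of wording and slightly more programming in SPSS, with no extra data. The model relies on data being missing at random, which is weaker than missing completely at random but still cannot be tested.
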